6.3. Lifestyle Restrictions

Not applicable.

6.4. Screen Failures

Individuals who do not meet the inclusion/exclusion criteria in this study (screen failure) may be rescreened. Individuals may be rescreened up to 3 times. The interval between screening failure and rescreenings should be at least 1 week. Each time rescreening is performed the individual must sign a new ICF or assent form (as applicable) and will be assigned a new identification number.

Screen failures are defined as patients who consent to participate in the clinical study but are not subsequently assigned to study intervention. A minimal set of screen failure information is required to ensure transparent reporting of screen failure patients to meet the Consolidated Standards of Reporting Trials (CONSORT) publishing requirements and to respond to queries from regulatory authorities. Minimal information includes demography, screen failure details, eligibility criteria, and any SAE.

7. Treatments

7.1. Treatments Administered

Lilly (or designee) will provide the following primary study materials:

- Tablets containing 1 mg of baricitinib
- Tablets containing 2 mg of baricitinib
- Tablets containing 4 mg of baricitinib
- Liquid suspension containing baricitinib at 2 mg/mL strength

Baricitinib will be dosed as tablets or oral suspension based on patient weight and eGFR. The dosages will be adjusted according to [Table JAJE.5](#). Tablets are not to be split for the purpose of dose adjustment. Patients with weight <40 kg will receive baricitinib tablets or oral suspension orally based on patient choice. Patients with weight ≥ 40 kg are recommended to receive tablets only. Patients need to use same formulation (tablet or suspension) throughout the study, but formulation change may be considered after discussion with Lilly or its designee depending on the reason.

The investigator or his/her designee is responsible for the following:

- explaining the correct use of the investigational agent(s) to the patient, parent/caregiver, or legal guardian,
- verifying that instructions are followed properly,
- maintaining accurate records of investigational product dispensing and collection
- at the end of the study returning all unused medication to Lilly, or its designee, unless Lilly and sites have agreed that all unused medication is to be destroyed by the site, as allowed by local law (see Section [7.5](#))

Patients or caregiver will be instructed to contact the investigator as soon as possible if he or she has a complaint or problem with the investigational product so that the situation can be assessed.

7.1.1. Packaging and Labeling

Baricitinib packaging will be labeled with a unique identifier for drug accountability. Baricitinib tablets and oral suspension will be provided in bottles. Baricitinib suspension will be supplied as a ready to use oral suspension and doses will be delivered to the patient using an oral syringe. Lilly will provide an instructions for use document that describes the process for administration of the suspension. The investigator or appropriate site personnel should review the instructions for use with the patient and parent/caregiver to ensure understanding of the correct administration procedure for the suspension.

Clinical study materials will be labeled according to the country's regulatory requirements.

7.2. Method of Treatment Assignment

All patients participating in this study will receive open-label baricitinib. Site personnel will dispense IP bottles manually. Site personnel will confirm that they have located the correct IP bottles before dispensing to the patient. Depending upon the prescribed dose and/or the visit frequency, baricitinib will be dispensed for sufficient supply until the next visit. If there is still a sufficient amount left in the patient's IP bottle until the next visit, the bottle will not be returned to site and the patient will take the IP from the same bottle. In this case, a new IP bottle will not be dispensed. The oral suspension formulation has a stability of 100 days after opening (breaking the seal).

7.2.1. Selection and Timing of Doses

The mean half-life of baricitinib is 12.5 hours in adult patients with RA. Early clinical pharmacology studies in adults showed that doses of 5 to 10 mg QD resulted in a mean daily time of baricitinib concentrations that exceed the IC₅₀ of IL-6 mediated STAT-3 phosphorylation of 2.5 to 7 hours. This suggests that in adults daily dosing will result in not only some daily time above the IC₅₀, but also some daily time without significant target engagement. As discussed in Section 9.4, the half-life- of baricitinib appears to be shorter in children compared with adults.

7.3. Blinding

This is an open-label study.

7.4. Dosage Modification

Refer to Section 5.1.1.

7.5. Preparation/Handling/Storage/Accountability

The investigator or designee must confirm appropriate temperature conditions have been maintained during transit for all study treatment received and any discrepancies are reported and resolved before use of the study treatment.

Only patients enrolled in the study may receive study treatment and only authorized site staff may supply or administer study treatment. All study treatment must be stored in a secure, environmentally controlled, and monitored (manual or automated) area in accordance with the labeled storage conditions with access limited to the investigator and authorized site staff.

The investigator, institution, or the head of the medical institution (where applicable) is responsible for study treatment accountability, reconciliation, and record maintenance (that is, receipt, reconciliation, and final disposition records).

All investigational product (used and partially used) will be returned to Lilly or destroyed at the site level with Lilly's written approval. In some cases, sites may destroy the material if, during the investigative site selection, the evaluator has verified and documented that the site has appropriate facilities and written procedures to dispose of clinical trial materials.

Follow storage and handling instructions on the IP packaging.

7.6. Treatment Compliance

Patient compliance with study medication will be assessed at each visit during the treatment period (dose adjustment period, primary treatment period and maintenance treatment period). Compliance will be assessed by counting returned tablets or weighing a returned bottle for liquid suspension.

Patients treated with baricitinib will be considered noncompliant if they miss $\geq 20\%$ of the prescribed doses during the study (unless the patient's investigational product was withheld by the investigator for safety reasons).

Similarly, patients will be considered noncompliant if they are judged by the investigator to have intentionally or repeatedly taken more than the prescribed amount of study medication. Patients found to be noncompliant per investigator judgment should be assessed to determine the reason for noncompliance and educated and/or managed as deemed appropriate by the investigator to improve compliance.

Patients will be counseled by study staff on the importance of taking the investigational product as prescribed, as appropriate.

Patient compliance will be further defined in the statistical analysis plan.

7.7. Concomitant Therapy

All concomitant medication taken during the study must be recorded on the Concomitant Medication electronic case report form (eCRF).

Patients will be instructed to consult the investigator or other appropriate study personnel at the site before taking any new medications or supplements during the study.

Additional drugs are to be avoided unless required to treat AEs or for the treatment of an ongoing medical condition. If the need for other concomitant medications arises, discontinuation of the patient from the investigational product or the study will be at the discretion of the investigator in consultation with Lilly or its designee (Section 8.2).

Treatment with concomitant therapies for NNS/CANDLE, SAVI, or AGS during the study is permitted, but treatments as prohibited in the section of exclusion criteria (Section 6.2) are still prohibited during the study.

For patients who discontinued or completed study treatment and have entered the post-treatment follow-up period, particular therapies for NNS/CANDLE, SAVI, or AGS (ie, immunosuppressive biologic agent, monoclonal antibody, JAK inhibitor) should not be used during the post-treatment follow-up period. However, their therapies are allowed if the investigator determines them to be appropriate.

7.7.1. Concomitant Therapy during pre-treatment period for NNS/CANDLE patients

Patients will remain on their treatments for NNS/CANDLE therapy (excluding JAK inhibitors) during pre-treatment period based on investigator's discretion. For NNS/CANDLE patients who have previously been treated with JAK inhibitors and/or biologic agents/monoclonal antibodies therapy prior to the study, JAK inhibitors are stopped at Visit 1. Biologic agents/monoclonal antibodies are stopped with an appropriate washout duration prior to Visit 6 (see Section 6.2 Exclusion criteria [27]).

7.7.2. Systemic corticosteroid

The use of systemic corticosteroid for NNS/CANDLE, SAVI, or AGS is permitted through the study. Steroid weaning may begin at Visit 6 according to Section 5.1.1. Even if the steroid weaning is conducted, the dose of steroid is permitted to increase after the weaning if medically necessary in the opinion of the investigator. In this case, it is recommended that the dose of steroid is not greater than that of baseline (dose at Visit 6). However, it is allowed to exceed the dose of baseline temporarily if the patient is experiencing unacceptable or worsening symptoms of NNS/CANDLE, SAVI, or AGS. The reason for steroid dose change will be documented in the medical record.

7.8. Treatment after the End of the Study

After end of the study, continued access to baricitinib will not be provided.

8. Discontinuation Criteria

8.1. Discontinuation from Study Treatment

8.1.1. Permanent Discontinuation from Study Treatment

In rare instances, it may be necessary for a patient to permanently discontinue (definitive discontinuation) study intervention. When necessary, a participant may be permanently discontinued from study intervention. If so, the participant will remain in the study and follow procedures for remaining study visits, as shown in the Schedule of Activities (see Section 2).

Possible reasons leading to permanent discontinuation of investigational product:

Laboratory test results

Hepatic event or Liver test abnormality. A patient who is discontinued from investigational product due to a hepatic event or liver test abnormality should have additional hepatic safety data collected via eCRF.

Discontinuation of the investigational product for abnormal liver tests should be considered by the investigator when a patient meets one of the following conditions after consultation with Lilly or its designee:

- ALT or AST $>8 \times$ ULN
- ALT or AST $>5 \times$ ULN for more than 2 weeks after temporary interruption of investigational product
- ALT or AST $>3 \times$ ULN and total bilirubin (TBL) $>2 \times$ ULN or international normalized ratio (INR) >1.5
- ALT or AST $>3 \times$ ULN with the appearance of fatigue, nausea, vomiting, right upper-quadrant pain or tenderness, fever, rash, and/or eosinophilia ($>5\%$)
- Alkaline phosphatase (ALP) $>3 \times$ ULN that is deemed to be of liver origin and drug related
- ALP $>2.5 \times$ ULN and TBL $>2 \times$ ULN
- ALP $>2.5 \times$ ULN with the appearance of fatigue, nausea, vomiting, right quadrant pain or tenderness, fever, rash, and/or eosinophilia ($>5\%$)

Other Laboratory Abnormality Results

Discontinuation of the investigational product should be considered by the investigator when a patient meets one of the following conditions after consultation with Lilly or its designee:

- WBC count <1000 cells/ μ L
- ANC <500 cells/ μ L
- lymphocyte count <200 cells/ μ L
- hemoglobin <6.5 g/dL

Note: If any of the above specific abnormalities are considered a feature of the disease (NNS/CANDLE, SAVI, or AGS) and the investigator determines that it is in the best interest of the patient to continue treatment, patients may continue the investigational product. The reason for the decision will be documented in the medical record after discussion with Lilly or its designee.

Note: Temporary interruption rules (see Section 8.1.2) must be followed where applicable. However, if, in the opinion of the investigator, the laboratory abnormality is due to concurrent illness such as cholelithiasis or another identified factor, laboratory tests may be repeated. Only when the laboratory value meets resumption thresholds (Table JAJE.6) following the recovery from the concurrent illness or other identified factor may the investigator restart investigational product, after consultation with Lilly or its designee.

Other circumstances

In addition, patients will be discontinued from the investigational product in the following circumstances:

- The patient enrolls in any other clinical trial involving an investigational product or in any other type of medical research judged not to be scientifically or medically compatible with this study.
- Investigator/Physician Decision:
 - An SAE or a clinically significant change in a laboratory value occurs that, in the opinion of the investigator, merits the investigational product being discontinued and appropriate measures being taken. In this case, Lilly or its designee is notified immediately. Refer to Safety Evaluations (Section 9.2).
 - The investigator decides that the patient should be withdrawn from the study.
 - The patient, for any reason, requires treatment with another therapeutic agent that has been demonstrated to be effective for treatment of the study indication; discontinuation from the study occurs prior to introduction of the new agent.
- Parent, legal guardian, or patient decision:
 - The parents, legal guardian, or patient requests to be withdrawn from the study.
- Sponsor Decision:
 - Lilly stops the study or stops the patient's participation in the study for medical, safety, regulatory, or other reasons consistent with applicable laws, regulations, and GCP.
 - Investigational product will no longer be supplied if Lilly stops development of the compound for any reason at any time.
- Compliance:
 - Patients found to be noncompliant with investigational product should be assessed to determine the reason for noncompliance. Education as deemed appropriate by the investigator may be provided to improve compliance. Persistent noncompliance may result in the patient being discontinued from the study.
- Pregnancy (see Section 9.2.1).
- Malignancy.

- Develop a VTE event (DVT/PE) during the study.
- HBV DNA is detected with a value above the limit of quantitation (see Section 9.4.6).
- Confirmed diagnosis of *Pneumocystis* pneumonia during the study.

Patients discontinuing from the investigational product prematurely for any reason should complete AE and other follow-up- procedures per Section 2 (Schedule of Activities), Section 9.2 (Adverse Events), and Section 9.4 (Safety) of this protocol.

8.1.2. Temporary Discontinuation from Study Treatment

On occasion, the investigator may find it necessary to temporarily interrupt or prematurely permanently discontinue investigational product administration following the occurrence of an AE or an abnormal laboratory finding. Except in cases of emergency, it is recommended that the investigator consult with Lilly or its designee before temporarily interrupting or prematurely permanently discontinuing therapy. Based on investigator discretion, if significant changes from baseline in eGFR are observed, the lab test should be repeated and confirmed on 2 separate occasions and Lilly or its designee must be contacted to discuss and document the appropriate course of action which may include a nephrology evaluation.

As listed in Table JAJE.6, certain situations necessitate a discussion with Lilly or its designee about whether treatment should be continued, either at the same dose or with a dose decrease, or if treatment should be temporarily withheld. Although Table JAJE.6 outlines guidance for certain situations, a discussion with the Sponsor should occur about the best course of action and decisions should be documented. Follow-up- laboratory tests to monitor the abnormal finding should be done promptly and frequently at the discretion of the investigator. The investigator must obtain approval from Lilly or its designee before restarting investigational product that was temporarily interrupted for an AE or for an abnormal laboratory finding.

Table JAJE.6. Guidance on Interruption of Investigational Product

Hold investigational product if the following laboratory test results occur, unless continuation of investigational product is approved by Lilly or its designee with documentation:	If investigational product was stopped, it may be restarted after discussion with Lilly or its designee or when:
WBC count <2,000 cells/ μ L ^a	WBC count \geq 2,000 cells/ μ L
ANC <1,000 cells/ μ L ^a	ANC $>$ 2,000 cells/ μ L (Patients with baseline ANC counts between 1000 and 2000 cells/ μ L may restart investigational product when values return to baseline.)
Lymphocyte count <500 cells/ μ L ^a	Lymphocyte count \geq 500 cells/ μ L
Platelet count <75,000/ μ L ^a	Platelet count $>$ 100,000/ μ L (Patients with baseline platelet counts between 75,000 and 100,000/ μ L may restart investigational product when values return to baseline.)
Patients with eGFR <60 mL/min/1.73 m ² at assignment of initial dose eGFR <30 mL/min/1.73 m ² ^b	eGFR \geq 40 mL/min/1.73 m ²
Patients with eGFR \geq 60 mL/min/1.73 m ² at assignment of initial dose eGFR <40 mL/min/1.73 m ²	eGFR \geq 50 mL/min/1.73 m ²
ALT or AST $>$ 5 \times ULN or ALT or AST $>$ 3 \times ULN and total bilirubin $>$ 2 \times ULN	ALT and AST return to <2 \times ULN, and investigational product is not considered to be the cause of enzyme elevation.
Hemoglobin <8 g/dL ^a	Hemoglobin \geq 8 g/dL
Symptomatic HZ	All skin lesions have crusted and are resolving
Infection that, in the opinion of the investigator, merits the IP being interrupted	Resolution of infection
Clinical features of VTE (such as deep venous thrombosis or pulmonary embolism) are present ^c	After confirmation that DVT/PE is not present

Abbreviations: ALT = alanine aminotransferase; ANC = absolute neutrophil count; AST = aspartate aminotransferase; DNA = deoxyribonucleic acid; DVT = deep vein thrombosis; eGFR = estimated glomerular filtration rate; HBV = hepatitis B virus; IP = investigational product; PE = pulmonary embolism; ULN = upper limit of normal; VTE = venous thromboembolic event; WBC = white blood cell.

^a Investigational product can be continued if decrease in WBC, ANC, lymphocyte count, platelet count, or hemoglobin is determined to be disease related. The investigator must also consult with Lilly or its designee to continue the investigational product. For patients with hemoglobin values <8 g/dL who were previously evaluated by a hematologist and approved for enrollment by Lilly or its designee, interruption of the investigational drug will be considered if a decrease of >1.5 g/dL from the lowest recorded baseline hemoglobin occurs.

^b For patients with preexisting renal impairment, a lower threshold for interruption may be considered after discussion with Lilly or its designee.

- c Evaluate promptly and institute appropriate treatment. If upon evaluation VTE is ruled out and no other temporary or permanent discontinuation criteria are met, then investigational product may be resumed.

Although temporary interruption of investigational product is not a requirement at times of increased potential risk of VTE (eg, surgery, significant air travel, or other situations involving prolonged immobilization), following appropriate VTE prophylaxis guidelines is recommended to help manage the VTE risk under these circumstances.

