[18] Have any history of venous thromboembolic event (VTE) (deep vein thrombosis [DVT]/pulmonary embolism [PE]) prior to screening.

[19] Have a serious and/or unstable illness that, in the opinion of the investigator, poses an unacceptable risk for the patient's participation in the study.

[20] Have had any major surgery within 8 weeks prior to screening or will require major surgery during the study that, in the opinion of the investigator in consultation with Lilly or its designee, would pose an unacceptable risk to the patient if participating in the trial.

[21] Have screening laboratory test values outside the reference range that, in the opinion of the investigator, pose an unacceptable risk for the patient's participation in the study.

[22] Have any of the following specific abnormalities on screening laboratory tests (patients with NNS/CANDLE will be confirmed the eligibility again using the most recent laboratory test results prior to Visit 6).

- Aspartate aminotransferase (AST) or alanine aminotransferase (ALT) $>2 \times$ the upper limit of normal (ULN),
- Hemoglobin <10 g/dL (100 g/L),
- Total WBC count <2500 cells/ μ L,
- Neutropenia (absolute neutrophil count [ANC] <1200 cells/ μ L),
- Thrombocytopenia (platelets $<100,000/\mu$ L).

Note: The most recent visit prior to Visit 6 is defined as Visit 4 for patients without a biologic agent wash-out or Visit 5 for patient requiring biologic agent wash-out)

Note: A patient with NNS/CANDLE, SAVI, or AGS condition may be enrolled with any of the above specific abnormalities on laboratory tests if these laboratory abnormalities are considered a feature of the disease. If the laboratory abnormality is a feature of the underlying disease must be evaluated, in conjunction with the investigator, and documented; the investigator must also consult with Lilly or its designee before the patient can be enrolled.

[23] Have an eGFR based on serum creatinine at Visit 1 of <40 mL/min/1.73 m²:

- for patients less than 2 years of age (eGFR based on the Bedside Schwarz 2009 formula),
- for patients between 2 years and 18 years of age inclusive (eGFR based on the Japanese Society for pediatric Nephrology formula),
- for patients greater than 18 years of age (eGFR based on CKD-EPI Creatinine 2009 equation)

[24] Have screening thyroid-stimulating hormone and/or thyroxine values outside of the laboratory's reference range and are assessed, in conjunction with the investigator, to be clinically significant.

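### For patients enrolled with hemoglobin below 8 g/dL, the footnote's interruption trigger lies below the level at which Section 8.1.1 has permanent discontinuation considered, and the numeric restart level lies above their own baseline

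*Protocol*

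**What the plan says.** Exclusion criterion 22 (Protocol 6.2) bars hemoglobin below 10 g/dL, but its note says a patient "may be enrolled with any of the above specific abnormalities on laboratory tests if these laboratory abnormalities are considered a feature of the disease", after consultation with the sponsor. Patients with hemoglobin below 8 g/dL can enter by this route.

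The hold condition in Table JAJE.6 (Protocol 8.1.2) is "Hemoglobin <8 g/dL ^a", and the numeric restart condition is a value of at least 8 g/dL. The restart column also allows restart after discussion with the sponsor. Footnote a first permits treatment to continue, with sponsor consultation, if the decrease is judged disease related. It then turns to a special group, introduced with the words "For patients with hemoglobin values <8 g/dL who were previously evaluated by a hematologist and approved for enrollment by Lilly or its designee". The footnote sets a separate trigger there, a relative fall in place of the fixed level: "interruption of the investigational drug will be considered if a decrease of >1.5 g/dL from the lowest recorded baseline hemoglobin occurs".

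Protocol 8.1.1 lists "hemoglobin <6.5 g/dL" among the results at which the investigator should consider permanent discontinuation after consulting the sponsor. It gives no separate level for patients enrolled below 8 g/dL. A first note lets treatment continue if the abnormality is a feature of the disease. A second note covers abnormalities put down to concurrent illness or another identified factor, and makes restart depend on meeting the Table JAJE.6 resumption level.

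**The concern.** The two sections give the same patient two hemoglobin levels, and for this group the levels fall in the opposite order from everyone else's. Elsewhere a patient meets the hold level first and the level for considering a permanent stop later. Here the permanent-stop item is met while the footnote's own interruption trigger has not yet been reached. A site reading the footnote alone and a site reading 8.1.1 alone could act differently on the same value.

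Hemoglobin is a parameter where this could matter. Protocol 3.2 lists its decrease among the most common laboratory changes with the drug, anemia is an adverse event of special interest (Protocol 9.2.2), and SAP 6.12.3.1 defines it by the same 6.5 g/dL limit. A patient managed by the footnote's trigger alone would pass that limit first. The rules stay in force for as long as treatment continues, which can be to Week 244.

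**Working it through.** **Inputs**
- Lowest recorded baseline hemoglobin, B. The footnote's group has B < 8.0 g/dL (Table JAJE.6, footnote a).
- Footnote trigger: a fall of more than 1.5 g/dL, that is, a value below B − 1.5.
- Permanent discontinuation considered: below 6.5 g/dL (8.1.1).
- Ordinary hold: below 8 g/dL. Numeric restart: at least 8 g/dL (Table JAJE.6).

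**Order of the levels**

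If B < 8.0, then B − 1.5 < 8.0 − 1.5 = 6.5. The trigger is below 6.5 for every baseline in the group. The gap between the two levels is 6.5 − (B − 1.5) = 8.0 − B.

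**Restart**

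The numeric restart level exceeds baseline by 8.0 − B, the same quantity.

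The first-met columns assume that results are reported to 0.1 g/dL.

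| Baseline B | Footnote trigger | 8.1.1 item first met at | Footnote trigger first met at | 8.0 − B (gap between levels; restart excess over baseline) |
|---|---|---|---|---|
| 7.9 | <6.4 | 6.4 | 6.3 | 0.1 |
| 7.5 | <6.0 | 6.4 | 5.9 | 0.5 |
| 7.0 | <5.5 | 6.4 | 5.4 | 1.0 |
| 6.4 | <4.9 | already met at baseline | 4.8 | 1.6 |

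Checking every baseline from 5.0 to 7.9 in steps of 0.1 gives no exception. At B = 8.0 both levels are first met at 6.4. At B = 8.1 the trigger is first met at 6.5 and so comes before the 8.1.1 item.

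**Comparison with the protocol's other paired levels** (Table JAJE.6 hold, then 8.1.1)
- White cells: 2,000, then 1,000 cells/µL.
- Neutrophils: 1,000, then 500 cells/µL.
- Lymphocytes: 500, then 200 cells/µL.
- Hemoglobin, ordinary row: 8, then 6.5 g/dL.

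All four place the hold level first. Only the footnote group is reversed.

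**The case against.** Several points on the other side stand.

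- **Neither level is automatic.** Both steps are to be considered, with sponsor involvement, and Table JAJE.6 is presented as guidance. A reader might infer that a pause cannot come first for these patients. The documents do not say so: 8.1.2 lets the investigator interrupt for any adverse event or abnormal laboratory finding, and the footnote does not make a 1.5 g/dL fall the only ground.
- **The disease-feature notes may apply.** These patients enter through a disease-feature exception, and both 8.1.1 and footnote a allow treatment to continue when the abnormality or decrease is disease related. But a baseline anemia due to the disease does not make a later fall on treatment due to it. A fall not attributed to the disease is outside both notes.
- **Restart has a second route.** Discussion with the sponsor is an alternative to the numeric value, so these patients are not generally locked out. The exception is an abnormality put down to concurrent illness or another identified factor, where 8.1.1 ties restart to the resumption level.
- **The neutrophil and platelet rows are not a precedent.** They say certain patients "may restart investigational product when values return to baseline", and a reader might infer that the hemoglobin row omits a matching clause by oversight. Those clauses cover only baselines lying between the hold and restart levels. Hemoglobin has no such interval, and the clauses do not help a patient whose baseline is below the hold level.
- **The footnote can be read another way.** It might mean an on-study value below 8 in a patient approved with a baseline of 8 to below 10. For baselines of 8.1 to 9.9 the trigger would be 6.6 to 8.4, above 6.5, and the restart level would be below baseline, so neither problem arises. This reading is less natural. The wording links the value to approval for enrollment, and patients enrolled below 8 already meet the ordinary hold row at baseline, which explains why they need a separate trigger.

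**Conclusion.** The conflict is real on the natural reading of footnote a. For every baseline below 8 g/dL, the 8.1.1 level is met before the footnote's interruption trigger, by a margin of 8.0 − B (0.1, 0.5 and 1.0 g/dL at baselines of 7.9, 7.5 and 7.0). Below a baseline of 6.5 it is met from the start. The numeric restart level exceeds baseline by the same amounts. The conclusion assumes that the footnote refers to baseline hemoglobin. In practice it bites when a further fall is not attributed to the disease and, for restart, mainly when another cause has been identified.

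The practical reach is limited. About 5 patients are planned, and the documents do not show that anyone was enrolled below 8 g/dL. A reader might also infer that one such case would change who contributes Week 20 or Week 32 data. The documents do not support that: the SAP efficacy population is all enrolled patients with at least one dose, SAP 6.2 adds last observation carried forward, and 8.1.1 keeps permanently discontinued patients in the study for remaining visits. This is an inconsistency between safety instructions, not a threat to the efficacy analysis.

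**What to change.** Reconcile three places for patients enrolled with hemoglobin below 8 g/dL: footnote a to Table JAJE.6, the hemoglobin row of that table (both the hold and the restart cells), and the 6.5 g/dL item in Section 8.1.1. State in footnote a whether the value below 8 g/dL is the baseline or an on-study result. State which restart condition applies to this group, including after a concurrent illness or another identified factor. The sponsor's physician decides the levels and their order.

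The cost is protocol wording in one table row, one footnote and one list item, with the linked restart note in 8.1.1 checked for consistency. No new test is needed.
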